4.0 TREATMENT PLAN

4.1 **Treatment Dosage and Administration**

Prior studies in food-allergic subjects suggest that two standard (420 mg) doses (two days) of ibrutinib, an irreversible BTK inhibitor, are sufficient to completely inhibit BAT and suppress food SPT wheal size by an average of 77% (44% of all food SPTs became negative) (16). Additional doses of ibrutinib (up to 7 days) did not offer further suppression of SPTs, and BAT remained completely abolished for the duration of treatment. Therefore, we propose to extend these findings to acalabrutinib, another selective irreversible BTK inhibitor. Ten subjects will take acalabrutinib 100 mg twice daily by mouth (every 12 hours) for 2 days. Each subject will be enrolled for a minimum of 3 months (including the follow-up visit for toxicity monitoring).

Acalabrutinib is approved as a daily medication for another indication, and we propose to use the drug in adults only at its approved oral dosing of 100 mg twice daily for a maximum of two days. Dose limiting events include grade 3 or 4 hematologic events, grade 3 or 4 hepatotoxicity, AST or ALT >3 times normal range, creatinine > 2.5 times normal range. Dose-limiting toxicity (DLT) evaluation will be performed throughout the study.

The capsules should be swallowed intact with water. Subjects should not attempt to open capsules or dissolve them in water. Acalabrutinib can be taken with or without food.

If a dose is missed, it can be taken up to 3 hours after the scheduled time with a return to the normal schedule with the next dose. If it has been > 3 hours, the dose should not be taken and the subject should take the next dose at the scheduled time. The missed dose will not be made up and must be returned to the site at the next scheduled visit.

In healthy volunteers, co-administration with CYP3A inhibitors increased C_{max}, and therefore the drug will not be concomitantly administered with strong inhibitors or inducers of CYP3A.

4.2 **Toxicities and Dosing Delays**

Although toxicity is not expected given that subjects will only receive two days of drug, any subject who receives treatment on this protocol will be evaluable for toxicity. Each subject will be assessed for the development of toxicity according to the Time and Events table (Section 5.4).

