At each visit, subjects will be monitored for toxicities. This study will follow the FDA Guidance For Industry ("Toxicity grading scale for healthy adult and adolescent volunteers enrolled in preventative vaccine clinical trials") grading system for adverse events (17). If a subject develops a grade 3 or 4 nausea, vomiting, diarrhea, hematologic toxicity, renal toxicity, or hepatotoxicity, or any other Grade 4 toxicity or unmanageable Grade 3 toxicity, the medication will be stopped. Protocols for specific toxicities are listed below.

Hematological Toxicities: ANC < 1,500/µL or platelets < 100,000/µL will result in discontinuation of protocol therapy.

Renal Toxicity: Creatinine will be monitored per protocol. Creatinine levels >2.5 times the normal limit will result in discontinuation of protocol therapy.

Hepatotoxicity: Grade 3 hepatotoxicity, or an increase in AST or ALT >3 times upper limit of normal, will result in discontinuation in protocol therapy.

4.3 **Concomitant Medications/Treatments**

At the systemic exposure levels expected in this study, acalabrutinib inhibition of CYP metabolism is not anticipated.

However, acalabrutinib is metabolized by CYP3A. Concomitant administration of acalabrutinib with a strong CYP3A and P-glycoprotein (P-gp) inhibitor, itraconazole increased exposure by approximately 5-fold. Conversely, concomitant administration of acalabrutinib with a strong CYP3A inducer, rifampin, decreased acalabrutinib exposure and could reduce efficacy. Consequently, the concomitant use of strong inhibitors/inducers of CYP3A should be avoided when possible.

If medically justified, subjects may be enrolled if such inhibitors or inducers can be discontinued or alternative drugs that do not affect these enzymes can be substituted within 7 days before first dose of study drug.

The effect of agents that reduce gastric acidity (eg. proton pump inhibitors or antacids) on acalabrutinib absorption was evaluated in a healthy volunteer study (ACE-HV-004). Results from this study indicate that subjects should avoid the use of calcium carbonate containing drugs or supplements for a period of at least 2 hours before and at least 2 hours after taking acalabrutinib. Use of omeprazole, esomeprazole, lansoprazole or any

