5.1.10 Serum chemistries

Comprehensive metabolic panel (CMP) to include: albumin, alkaline phosphatase, ALT/SGPT, AST/SGOT, BUN, creatinine, electrolytes (sodium, potassium, calcium, chloride, bicarbonate), glucose, and total bilirubin.

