Appendix 1: Pill Diary

		монтн				
Sunday	Monday	Tuesday	Wednesday	Thursday	Friday	Saturday
Н	4					
-						L
		L				L

The study coordinator will fill in the month and days.

Please document number of pills and time you took the ibrutinib.

STATISTICAL ANALYSIS PLAN

Study Design and Endpoints

This is an open label study of acalabrutinib in 10 food-allergic adults to determine the effect of pretreatment (100 mg twice daily for 4 doses total) with acalabrutinib on food allergen reactivity in foodallergic subjects. There are 3 planned study visits where endpoint assessments will be collected. The primary endpoint will be assessed at Visit 1 (baseline) and Visit 2 (after acalabrutinib). Secondary and exploratory endpoints will be assessed at Visits 1, 2, and 3 (follow-up).

Primary endpoint: Change in subjects' threshold dose of peanut protein to elicit an objective clinical reaction

Secondary endpoints:

- 1. Change in size of skin prick test wheal
- 2. Change in percent of ex vivo basophil activation to anti-IgE and peanut, as determined by CD63 expression

Safety considerations and toxicity monitoring: Laboratory testing (complete blood counts, serum chemistries) and electrocardiogram

Given the nature of the study, it will be stopped if >50% of patients have a DLT as described in the protocol.

Sample Size and Power Analysis

Sample size was calculated based on the primary endpoint, assuming that the difference in threshold from baseline to after acalabrutinib is normally distributed with a standard deviation of 1.1 natural log units. Therefore, 10 subjects allows for 80% power to detect a 3-fold increase (1.1 natural log units; i.e. 1 food dose escalation) in the threshold food dose, using a paired t test with p<0.05 as an approximation. though non-parametric tests will be utilized in the final analysis if needed.

Data Analysis

As this is an open label trial, each subject's responsiveness will be examined compared to themselves (at baseline) prior to initiation of treatment. Descriptive statistics will be used to analyze endpoints. The primary endpoint will be analyzed by log transformation and paired t test with p value < 0.05, if appropriate. If assumptions for paired t test are violated, a Wilcoxon non-parametric sign test will be used.

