Secondary endpoints will be analyzed using ANOVA with repeated measures across all visits with p value < 0.05. For experiments with multiple dosing levels, we will first examine if there is a dose-level by treatment interaction. If there is an interaction, treatment effects in individual dosing levels will be examined. Non-parametric tests will be utilized in place of ANOVA if necessary. Corrections will be made for multiple comparisons, if applicable, using a Šídák or Bonferroni multiple comparisons correction with an alpha threshold of 0.05.

For safety endpoints, ANOVA will be used for analysis of individual laboratory values (blood counts or chemistries).

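### The only laboratory safety analysis stated in the SAP is a test of means, and no count of subjects past the protocol's own laboratory limits is planned

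*Combined protocol and SAP*

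**What the plan says.** In the SAP, under Data Analysis, the last sentence covers laboratory safety: "For safety endpoints, ANOVA will be used for analysis of individual laboratory values (blood counts or chemistries". The preceding paragraph names the form for other endpoints, "Secondary endpoints will be analyzed using ANOVA with repeated measures across all visits", then shortens it: "Non-parametric tests will be utilized in place of ANOVA if necessary". CBC and CMP are taken from the same 10 subjects at three visits (protocol 5.4).

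The protocol defines laboratory toxicity subject by subject. Section 4.1: "Dose limiting events include grade 3 or 4 hematologic events, grade 3 or 4 hepatotoxicity, AST or ALT >3 times normal range". Section 4.2 sets numerical limits for ANC (below 1,500/µL), platelets (below 100,000/µL) and AST/ALT (above 3 times the upper limit of normal), and for creatinine: "Creatinine levels >2.5 times the normal limit will result in discontinuation of protocol therapy".

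The SAP counts affected subjects only for its stopping rule on dose-limiting toxicity. It gives no method for adverse events. Protocol 10.3 says only that they will be handled by methods similar to those for the efficacy measures.

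**The concern.** Two things stand out. First, the within-subject form is named for secondary endpoints but not for laboratory values from the same subjects at the same visits. The own-baseline statements do not settle this. Protocol 10.0 and the SAP speak of responsiveness, and 10.3 lists skin test, basophil and challenge results, not laboratory values.

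Second, and more important, comparing visit means answers a different question from the one the protocol's limits ask. Toxicity is likely to appear as one or two subjects crossing a limit, not as a shift in the average. At stake is the safety report: a finding of no significant change in laboratory values could be read as evidence of laboratory safety when it says almost nothing about a single affected subject.

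**Working it through.** **The plan's own figure.** The only computed figure is the 80% power of the primary paired t test. With n = 10, difference 1.1 and SD 1.1 natural log units, the noncentrality is (1.1/1.1)·√10 = 3.16 on 9 df. Two-sided alpha 0.05 gives 0.803. The figure reproduces, and this point does not touch it. The plan gives no figure for the safety analysis.

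**Inputs.** From the documents: 10 subjects, three visits. Assumed, because the documents do not give them: total SD 1, equal correlation ρ between visits (0.3 to 0.8), and any change confined to Visit 2.

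**The two readings.** Both share the numerator SS(visit)/2.
- One-way: denominator SS(within visit)/27, critical F(2, 27) = 3.35.
- Repeated measures: denominator SS(residual)/18, critical F(2, 18) = 3.55.

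With no true change, the numerator has expectation 1 − ρ. The repeated-measures denominator also has expectation 1 − ρ. The one-way denominator has expectation 1, because it keeps the between-subject variance, so the one-way test is conservative.

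**Why one subject is invisible.** Let one subject fall by d at Visit 2.
- The visit mean moves by d/10, so SS(visit) rises by 10·(d/10)²·(2/3) = d²/15. The numerator mean square rises by d²/30.
- That subject's own within-subject SS rises by (2/3)d². The residual takes (2/3 − 1/15)d² = 0.6d². The denominator mean square rises by 0.6d²/18 = d²/30.

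Numerator and denominator rise by the same amount, whatever d is, so a single affected subject does not push the repeated-measures F upward on balance.

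**Simulation** (100,000 runs per cell, alpha 0.05, percent of trials rejecting):

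| Situation | Test | ρ 0.3 | ρ 0.5 | ρ 0.7 | ρ 0.8 |
|---|---|---|---|---|---|
| No change | one-way | 1.8 | 0.6 | 0.1 | 0.02 |
| No change | repeated measures | 5.0 | 4.9 | 5.1 | 5.0 |
| All subjects shift 0.5 SD | one-way | 12 | 9 | 6 | 4 |
| All subjects shift 0.5 SD | repeated measures | 23 | 30 | 48 | 66 |
| One subject falls 2 SD | repeated measures | 4.8 | 4.8 | 4.5 | 4.0 |
| One subject falls 3 SD | repeated measures | 4.5 | 4.2 | 3.4 | 2.5 |
| One subject falls 3 SD | one-way | 2.0 | 0.9 | 0.2 | 0.05 |
| One subject falls 3 SD | paired Visit 2 − Visit 1 | 4.2 | 3.9 | 2.8 | 1.9 |

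**Tied to the limits, with assumed values.** Take ANC mean 4,000 and SD 1,500, with one subject at 1,000: (4,000 − 1,000)/1,500 = 2 SD below the mean. Take platelets mean 250,000 and SD 60,000, with one subject at 80,000: (250,000 − 80,000)/60,000 = 2.8 SD below. Both subjects are past the Section 4.2 limit. At ρ 0.5 to 0.9 (20,000 runs each), repeated measures is significant in 2.8 to 4.7% of trials for ANC and 1.5 to 4.2% for platelets. One-way is significant in 0 to 1.0%.

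**What a count would show.** The exact upper 95% limit for 0/10 is 1 − 0.025^(1/10) = 30.8%. For 1/10 the interval is 0.3 to 44.5%, and for 2/10 it is 2.5 to 55.6%.

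**The case against.** The best reply is that most of this is already covered. The trial has one arm, so visit is the obvious factor, and the SAP itself uses the bare term for its repeated-measures test. Objective 2.2.1 sets out to describe adverse event frequency and severity. Its endpoint in 2.3 names cytopenias, hepatotoxicity and renal toxicity, and 8.1.1 counts an abnormal laboratory finding as an adverse event. Events are graded (8.1.2) and described one by one (8.3), reasons for stopping are documented (4.5, 5.5), and both 10.3 and the SAP promise descriptive statistics. With 10 subjects, a listing may tell nearly as much as a table.

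Much of this stands. A reader might infer that the SAP prescribes a between-subject ANOVA. The documents do not support that: the form is left unnamed, and shorthand is the likelier explanation. A reader might also infer that one subject's toxicity would go unreported. That too goes further than the text, since laboratory toxicity would probably appear among the adverse events.

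What remains is narrower. The descriptive promise is generic, with no table, threshold or denominator. The adverse event method in 10.3 refers back to a paired t test and its non-parametric substitute, which are not frequency methods. The one laboratory method that the SAP does state cannot show what Sections 4.1 and 4.2 define as toxicity.

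**Conclusion.** The point holds as a minor one. The missing tabulation matters under either reading of ANOVA. With a 2 to 3 SD fall in one subject, repeated measures rejects in about 2 to 5% of trials, no more than its null rate. The loss from a literal one-way analysis (true size about 0.6% or less at ρ of 0.5 or more) arises only if the sentence is taken at its word, which is the less likely reading.

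The percentages rest on assumed correlations, equal correlation between visits, and assumed ANC and platelet distributions. The equal rise of d²/30 in both mean squares depends only on 10 subjects, three visits and one affected subject at one visit.

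The consequence is confined to the safety report. It would be wrong to infer that subjects are less protected: monitoring, discontinuation and stopping rules work on individual values and do not use this test. Whether the rule beginning "Corrections will be made for multiple comparisons, if applicable" covers the laboratory tests, and how the EKG listed under safety will be summarised, are side issues.

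**What to change.** Replace the SAP safety sentence with:

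> Each laboratory value will be summarised as within-subject change from baseline with paired 95% CIs (or by ANOVA with repeated measures), and p-values will be descriptive. Among subjects who received at least one dose, the number crossing each existing numerical Section 4.2 limit (ANC, platelets, creatinine, AST/ALT) will be tabulated by visit with exact 95% CIs.

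The count is the essential part, because the paired comparison alone is as blind to one subject as the ANOVA. The denominator is the safety set already defined in 6.1.

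In protocol 10.3, replace the adverse event sentence with number and percent of subjects by event and worst grade. Before that, reconcile the two grading scales: 4.2 and 8.1.2 name the FDA scale for vaccine trial volunteers, and 11.3 names the NCI criteria. Before any Visit 3 contrast is defined, reconcile the follow-up time, which is 30 days in 4.5 and 5.4 but 3 months in 5.3.

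The cost is two sentences in the SAP, one in 10.3 and a little more tabulation. All the data are already collected. The intervals will be wide at n = 10. No limit or clinical rule changes.
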